3.2.1.3 Disease Control Rate (DCR)

DCR is defined as the proportion of patients with a BOR of either CR, PR or SD for at least 16 weeks post-baseline (corresponding to SD for 2 scheduled scans post-baseline). As the protocol allows a window of 1 week for the scan, a time window of 1 week before the Week 16 visit will be applied such that any scan that is at least 15 weeks after starting treatment will be considered acceptable for the evaluation of response. DCR was set as primary efficacy endpoint for arm A and secondary efficacy endpoint for arm B. As an additional analysis, DCR will also be defined as the proportion of patients with a BOR of either CR, PR or SD for at least 8 weeks post-baseline (corresponding to SD for 1 scheduled scan post-baseline). As the protocol allows a window of 1 week for the scan, a time window of 1 week before the Week 8 visit will be applied such that any scan that is at least 7 weeks after starting treatment will be considered acceptable for the evaluation of response.

3.2.1.4 Percentage change in the sum of target lesions

Percentage change in sum of diameters of target lesions from baseline for patients with measurable disease, will be calculated for each RECIST assessment visit, as follows:

Percentage change in the sum of target lesions (%) = $(\Sigma \text{ observed value after baseline} - \Sigma \text{ observed value at baseline}) * 100 / \Sigma \text{ observed value at baseline}$

Percentage change in sum of diameters of target lesions was set as a secondary efficacy endpoint for both arm A and arm B.

The best overall percentage change in the sum of target lesions (%), representing the largest decrease (or smallest increase in the absence of a decrease) from baseline, will also be considered as an efficacy endpoint.

3.2.1.5 Progression Free Survival (PFS)

PFS is defined as the time from first dose of study treatment (Day 1) until the date of disease progression or death (by any cause in the absence of progression), regardless whether the patient withdraws from the assigned study treatment or receives another anticancer prior to progression.

Patients who have not progressed or died at the time of analysis will be censored at the time of the latest date of RECIST 1.1 assessment of their last evaluable scan, however if the patient progresses or dies after 2 or more missed scheduled scanning visits (Progression/Death date - Last available scan date \geq 16 +1 weeks), the patient will be censored at the time of their last evaluable scan prior to the missing scan visits. If the patient has no evaluable visits or does not have baseline data, they will be censored at 0 days. However, if the patient dies within 2 scan visits of first dose (within 16 +1 weeks from first dose date without a post baseline scan) then its death date will be treated as their progression date. PFS was set as secondary efficacy endpoint both for arm A and arm B, and PFS time is defined as:

$$\text{PFS (days)} = \text{Date of documented PD, Death or last RECIST 1.1 assessment} - \text{first dose of study treatment (C0D1)} + 1$$

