RECIST 1.1 assessments (by CT/MRI) n		X		On study tumour assessments should occur q8w +/- 1 week (relative to first dose of IP) for the first 56 weeks, followed by q12w +/- 1 week until RECIST1.1 radiological progression x				On study tumour assessments should continue q8w +/- 1 week (relative to first dose of IP) for the first 56 weeks, followed by q12w +/- 1 week until RECIST1.1 radiological progression q, x				If a patient discontinues for a reason other than progression then tumour assessments should continue q8w +/- 1 week (relative to first dose of IP) for the first 56 weeks, followed by q12w +/- 1 week until RECIST1.1 radiological progression					
CCI h (mandatory unless unavailable at site) i		X*		On study CCI h assessments should occur at week 8 and week 16 +/- 1 week relative to first dose of IP.			On study CCI h assessments should occur at week 8 and week 16 +/- 1 week relative to first dose of combination										
Vitamin D3 and Calcium supplements			Patients should commence 800 IU vitamin D3 (Cholecalciferol) daily and 1000-1500 mg calcium daily supplements from ICF signature until RXC004 discontinuation														
Denosumab dosing y			120 mg sc Denosumab once every month from C0D1 until RXC004 discontinuation														
RXC004 dosing m			X (2 mg single dose)	Continuous daily dosing (2 mg QD)			Continuous daily dosing (1.5 mg QD)										
RXC004 diary			X	Review at each visit													

Table 1 – Arm A Schedule of assessments

Treatment Phase	Pre-treatment		RXC004 monotherapy			RXC004 + nivolumab combination j		Post-treatment				
	Pre-Screening	Screening	Cycle 0 (3-7 days)	Cycle 1 (28 day cycle)		Cycle 2 onwards (28 day cycles)	Pre-first Cycle	Cycle 1 onwards (28 day cycles)	IP Discontinuation	30 day Follow-up v	90 day Follow-up v	Survival follow-up
Window	n/a	-28 to -1	D1	D1	D15 +/- 1d	D1 +/- 3d		D1 +/- 3d	Within 7 days	+/- 3d	+/- 3d	q8w +/- 1wk
Nivolumab dosing								480 mg q4w +/- 3 days o				
RXC004 PK f			X		X	X		X	X			
Concomitant medication		X	X	X	X	X	X	X	X	X	X	
Adverse events		X	X	X	X	X	X	X	X	X	X	
Taste assessment z		X	At each visit – only if patient reports dysgeusia									
Survival status and post-discontinuation anti-cancer therapy p										X	X	X

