## 4 STUDY DESIGN

### 4.1 Overall Design

This is Phase II, open label, multicentre, multi-arm, study to evaluate the preliminary efficacy and safety of RXC004 as monotherapy and in combination with nivolumab in patients with Ring finger protein 43 (RNF43) or R-spondin (RSPO) aberrated, microsatellite stable (MSS), colorectal cancer (CRC), that have progressed following current standard of care treatment.

The study is composed of two arms, RXC004 monotherapy (Arm A) and RXC004 in combination with nivolumab (Arm B). 20 evaluable patients will be enrolled in Arm A and 20 evaluable patients in Arm B.

The study initially opened with Arm A; Arm B will be opened once a recommended Phase II dose (RP2D) for RXC004 in combination with nivolumab is established in the Phase I dose escalation study (NCI 03447470). A safety review of the combination data will be conducted after █ patients have received the combination of RXC004 and nivolumab for at least 1 cycle.

Once Arm B is opened, patients who are eligible for both Arm A and Arm B will be randomised 2:1 to Arm B: Arm A in an open-label manner. Randomisation will be stratified by genetic alteration (RNF43 vs RSPO).

Patients in Arm A may be treated with RXC004 + nivolumab if they have progressive disease on the 8-week scan, as long as they are eligible for Arm B and have Sponsor approval.

Patients who have undergone dose reduction during monotherapy cannot have the RXC004 dose re-escalated if switching to RXC004 + nivolumab combination therapy. The RXC004 dose must be discussed with the Sponsor prior to starting combination therapy.

The primary objectives of the study are to assess the preliminary efficacy of each treatment arm; RXC004 monotherapy and RXC004+nivolumab based on an individual patients best overall response.) Tumour assessment will be performed by Investigators every 8 weeks ± 1 week (relative to the date of initiation of study treatment) for the first 56 weeks, followed by q12w weeks ± 1 until radiological disease progression (as defined by Response Evaluation Criteria in Solid Tumours, version 1.1 [RECIST1.1]). The primary efficacy endpoint for RXC004 monotherapy is disease control rate (i.e. proportion of patients who achieve CR, PR or SD) and the primary efficacy endpoint for RXC004 + nivolumab is objective response rate. Following radiological progression, patients will be followed-up for safety and survival.

The general study design is summarized in Figure 1.

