#### **9.4.2.2 Secondary Endpoint(s)**

Progression free survival is defined as the time from first dose of study treatment until the date of disease progression or death (by any cause in the absence of progression), regardless whether the subject withdraws from the assigned study treatment or receives another

anticancer prior to progression. Patients who have not progressed or died at the time of analysis will be censored at the time of the latest date of RECIST v1.1 assessment of their last evaluable scan, however if the subject progresses or dies after 2 or more missed scheduled scanning visits, the subject will be censored at the time of their last evaluable scan prior to the missing scan visits. If the subject has no evaluable visits or does not have baseline data they will be censored at 0 days unless they die within 2 scan visits of baseline. Progression free survival will be listed by subject and will be presented graphically using Kaplan-Meier plots. Median PFS, together with 3 month, 6 month and 12 months PFS rates will be estimated.

Percentage change in tumour size will be derived at each visit by the percentage change from baseline in the sum of diameters of target lesions. The best percentage change in tumour size will be the subjects value representing the largest decrease (or smallest increase) from baseline in tumour size. Best percentage change in tumour size will be presented in waterfall plots and percentage change in tumour size at each visit will be presented in a spider plot.

CC1  
CC1  
CC1  
CC1  
CC1  
CC1  
CC1  
CC1

Overall survival is defined as the time from first day of study treatment until death due to any cause. Any subject not known to have died at the time of analysis will be censored based on the last recorded date on which the subject was known to be alive. Overall survival will be listed by subject and presented graphically using Kaplan-Meier plots. Median, 6 month and 12 month OS rates will be estimated.

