target lesions should be selected on the basis of their size (lesions with the longest diameter), be representative of all involved organs, but in addition should be those that lend themselves to

reproducible repeated measurements. All other lesions including pathological lymph nodes should be identified as non-target lesions.

At each tumour assessment visit, the sum of the diameters (longest for non-nodal lesions, short axis for nodal lesions in mm) for all target lesions will be calculated. If lymph nodes are to be included in the sum, then as noted above, only the short axis is added into the sum.

The baseline sum diameters will be used as reference to further characterise any objective tumour regression in the measurable dimension of the disease. The minimum observed sum of diameters is called “Nadir” and this includes the baseline sum if that is the smallest observed on study. If a lesion split into different components, it will be considered as single lesion where the diameter is obtained by the sum of the longest diameter of each single component.

RECIST 1.1 guideline will be followed to determine the overall tumour response based on target lesions, non-target and new lesions responses. Tumour assessment visits will be conducted, in accordance with SoA (see protocol), every 8 weeks \pm 1 week (relative to the date of initiation of study treatment) for the first 56 weeks, followed by q12w weeks \pm 1 until radiological disease progression (as defined by Response Evaluation Criteria in Solid Tumours, version 1.1 [RECIST 1.1]).

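### SAP 3.2.1.5 codes two missed scans as a fixed 17-week gap, so some PFS events after a single missed scan are censored, chiefly once scans are 12-weekly

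*SAP*

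**What the plan says.** Protocol 9.4.2.2 states the rule as a visit count: "if the subject progresses or dies after 2 or more missed scheduled scanning visits, the subject will be censored" at the last evaluable scan before the gap. It gives no number of weeks.

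SAP 3.2.1.5 keeps the visit count in words and then defines it in brackets. The patient "progresses or dies after 2 or more missed scheduled scanning visits (Progression/Death date - Last available scan date" is at least "16 +1 weeks), the patient will be censored at the time of their last evaluable scan prior to the missing scan visits".

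The scan calendar in Protocol 1.2 is "q8w +/- 1 week (relative to first dose of IP) for the first 56 weeks, followed by q12w +/- 1 week until RECIST1.1 radiological progression". SAP 6.1 repeats the change of interval: "for the first 56 weeks, followed by q12w weeks". Nothing legible in either document adjusts the 17 weeks for the later schedule. The legible entries in SAP 4.15, which lists departures from the protocol, do not mention the PFS rule (one entry there is blacked out).

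SAP 4.11.3.2 plans Kaplan-Meier curves, the median, and PFS rates at 3, 6 and 12 months, with a month of 30.4375 days.

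**The concern.** A programmer will code the bracketed number, not the words before it. If 17 weeks does not mean two missed scans on the schedule in force, the SAP departs from the protocol rule that it claims to apply. An observed progression or death that the protocol counts as an event becomes a censored time at the previous scan. That censoring is informative: it is triggered by the event date itself. It leaves the Kaplan-Meier curve the same or higher from the date of the lost event onwards, which favours the drug. Protocol 4.3.1 says PFS will be weighed, with the other secondary endpoints, in deciding whether monotherapy goes forward.

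**Working it through.** **Inputs.** Scan calendar (Protocol 1.2, SAP 6.1): weeks 8, 16, 24, 32, 40, 48, 56, then 68, 80, 92 and so on, each +/-1 week. Trigger (SAP 3.2.1.5): 16 + 1 weeks. Month length (SAP 4.11.3.2): 30.4375 days. Evaluable patients: 20 per arm (Protocol 4.1). Median PFS cited for third-line standard of care: about 2 months (Protocol 2.3.3).

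**1. The plan's figure.** Two intervals plus one week: 2 x 8 + 1 = 17 weeks. The same construction gives 8 + 12 + 1 = 21 weeks across week 56 and 2 x 12 + 1 = 25 weeks on the 12-weekly schedule. So 17 belongs to the 8-weekly schedule only.

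**2. Progression found at the next scheduled scan.** Each scan can move by 1 week, so gap = nominal difference +/-2 weeks.

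| Scans missed | Example (weeks) | Nominal gap | Range | Result with 17 weeks |
|---|---|---|---|---|
| None, 8-weekly | 8 to 16 | 8 | 6-10 | event |
| None, 12-weekly | 56 to 68 | 12 | 10-14 | event |
| One, 8-weekly | 8 to 24 | 16 | 14-18 | censored only at 17-18 |
| One, week 56 missed | 48 to 68 | 20 | 18-22 | always censored |
| One, 12-weekly | 56 to 80 | 24 | 22-26 | always censored |
| Two, 8-weekly | 8 to 32 | 24 | 22-26 | always censored, as intended |

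**3. Share affected on the 8-weekly schedule.** Assume both scan dates are independent and uniform over their windows, and let D be their difference in weeks, between -2 and 2. Then P(16 + D >= 17) = P(D >= 1) = (2 - 1)^2 / 8 = 0.125. In whole days, 36 of the 15 x 15 = 225 date pairs differ by 7 days or more in that direction, which is 0.16.

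**4. Deaths after one missed scan, nominal dates.**
- 8-weekly: gap 8 to 16 weeks, never censored.
- 12-weekly: gap 12 to 24 weeks. Under 17 it is an event; from 17 it is censored, which is 24 - 17 = 7 of the 12 weeks.
- Week 56 missed: gap 8 to 20 weeks, censored for 20 - 17 = 3 of the 12 weeks.

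**5. Where on the curve.** Twelve months is 12 x 30.4375 / 7 = 52.2 weeks. In Arms A and B the clock starts at first dose.
- 12-weekly cases: the last scan is at week 56 - 1 = 55 at the earliest. The patient is at risk at week 52.2 under either rule, so the 12-month rate is identical.
- Week 56 missed: the patient leaves the risk set at weeks 47 to 49 instead of having an event at week 67 or later. Neither rule gives that patient an event by week 52.2. The smaller risk set leaves the 12-month rate unchanged or slightly lower.
- 8-weekly cases at 17 to 18 weeks: counting from a post-baseline scan, the earliest event is at week 7 + 17 = 24. These can raise the 6-month rate (26.1 weeks), the 12-month rate, or a median lying that late. The 3-month point (13.0 weeks) comes before any of them.

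**6. How many patients.** With exponential PFS and median m weeks, S(56) = 2^(-56/m). For medians of 2, 3 and 4 months (8.70, 13.04 and 17.39 weeks), S(56) = 1.2%, 5.1% and 10.7%. Times 20, that is 0.2, 1.0 and 2.1 patients per arm still event-free at week 56. The 2-month value is the cited one; 3 and 4 months are an assumed range. The documents give no missed-scan rate.

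**The case against.** The best defence is that one week of slack is a choice of tolerance. On nominal dates the 17-week rule classifies every single missed scan correctly on the 8-weekly schedule, for progressions and deaths alike, and most follow-up should fall there. PFS is secondary, with no model (SAP 4.11.1.2) and no formal comparison between arms (SAP 4.2.6). The cut-off is about 24 weeks after the last patient's Cycle 1 Day 1 (Protocol 9.4.1), so late enrolees may never reach 12-weekly scanning. PFS is also listed for every patient in the full analysis set, so an affected case can be found.

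All of that stands as a limit on size. It does not remove the contradiction: once scans are 12-weekly, the number and the words in the same sentence give different answers. With 20 patients in an arm, one reclassified event is 1/20 = 5 percentage points early on, and more in a thin tail.

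A reader might infer two stronger things. One is that every PFS event after one missed scan is lost once scans are 12-weekly. That fails: a death, or a progression found off schedule, less than 17 weeks after the last scan still counts. The other is that the 12-month rate is inflated by the change of schedule. In Arms A and B it is not, because week 52.2 comes before the affected events.

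**Conclusion.** Wrong as written, minor. The fixed gap contradicts the protocol's visit count. For a progression found at the next scheduled scan after one missed scan, the error is certain on the 12-weekly schedule and when week 56 is the missed scan. It is occasional on the 8-weekly schedule: about 12.5%, or 16% in whole days, given one missed scan and uniform windows. For 12-weekly deaths it applies at 17 to 24 weeks after the last scan.

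The 12-weekly and week-56 cases inflate the curve beyond about one year. Of the planned summaries in Arms A and B, only the 8-weekly cases can raise any, and by the dates above that means the 6- and 12-month rates or a late median. The statement is not made for Arm A2, whose efficacy baseline is the last scan before the switch (SAP 4.2.3). With a baseline at week 16, for example, its 12-month point falls at week 16 + 52.2 = 68.2, which takes in a week-68 progression.

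The expected effect is small: roughly 0.2 to 2 patients per arm reach week 56 event-free under the exponential assumption, and each must then miss a scan and have an event in the affected range. The primary endpoints are untouched.

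**What to change.** In SAP 3.2.1.5, delete the 16 + 1 week gap as the working definition. Count the scheduled scan visits (8-weekly to week 56, then 12-weekly, each with its +/-1 week window) missed between the last evaluable scan and the progression or death, and censor only if two or more were missed. State how a death inside an open window is counted.

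Do not swap in larger fixed gaps such as more than 18, 22 or 26 weeks, the upper ends of the one-missed-scan ranges above. They misclassify deaths and some gaps that span week 56. With the last scan at week 40, weeks 48 and 56 missed and death at week 60, two visits were missed and the protocol censors. The gap is only 20 weeks, so a 22-week threshold would count an event.

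The separate clause for deaths "within 16 +1 weeks from first dose date without a post baseline scan" can stay: it covers weeks 8 and 16 plus one week, where the 8-weekly figure fits. Counting visits also settles whether the baseline scan can be the last available scan. If it can, a missed week-8 scan with progression at week 16 gives a gap of about 15 to 21 weeks and may be censored after one miss.

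The cost is one sentence in the SAP and a small change to the PFS derivation. No new data are needed, and the protocol does not change.

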3.2.1.6 Overall Survival (OS)

OS is defined as the time from the first day of study treatment (Day 1) until death due to any cause. Any patient not known to have died at the time of analysis will be censored based on the last recorded date on which the patient was known to be alive. OS was set as secondary efficacy endpoint both for arm A and arm B, and OS time is defined as:

$$\text{OS (days)} = \text{Date of death or last contact} - \text{first dose of study treatment (C0D1)} + 1$$

3.2.2 Pharmacokinetic/Pharmacodynamic Variables

CCI

3.2.3 Safety Variables

The following safety variables will be evaluated:

- AEs and SAEs
- Dysgeusia
- Vital signs

- Electrocardiogram (ECG)
- ECOG performance status
- Prior and concomitant medications
- Clinical laboratory evaluation
- Bones evaluation

3.2.4 Exploratory Variables

Methods for evaluation of CCI [REDACTED] will be provided in a separate SAP.

4 STATISTICAL METHODS

4.1 Data Quality Assurance

Tables/Figures/Listings (TFLs) to be included in the report will be independently checked for consistency, integrity and in accordance with standard Parexel procedures.

4.2 General Presentation Considerations

All tables, listings, and graphs will be produced to landscape orientation using Courier New 9pt font and will be incorporated into a MS Word document as a rich text file (RTF) (margins on standard A4: Margins (top, left, right, and bottom) 2.54 cm.

4.2.1 Study Days

Screening will be conducted between Day -28 and Day -1. The first day of treatment will be Cycle 0 - Day 1 (C0D1). When calculating AEs/ConMeds/etc timing days will be calculated relative to day 1.

For patients in arm A, who have radiologically progressed at Week 8 and move to RXC004 + Nivolumab, count of days will re-start from the day of the first of intake of the combination a new Cycle 1 with D1, as reported in the Schedule of Activities (SoA) (see protocol).

4.2.2 Visit Windowing

By visit summaries will be made considering the windows as below. The visit windowing is assessed relative to C1D1 date (not C0D1 due to delays between C0D1 and C1D1).

C0D1	C0D1
C1D1	(C1D1 - Day 8)
Day 15	(Day 9 - Day 21)
Day 29	(Day 22 - Day 42)
Day 57	(Day 43 - Day 70)

Day 85	(Day 71 - Day 98)
Day 113	(Day 99 - Day 126)
Day 141	(Day 127 - Day 154)
Day 169	(Day 155 - Day 182)
Day 197	(Day 183 - Day 210)
Day 225	(Day 211 - Day 238)
Day 253	(Day 239 - Day 266)
Day 281	(Day 267 - Day 294)
Day 309	(Day 295 - Day 322)
Day 337	(Day 323 - Day 350)
Day 365	(Day 351 - Day 378)
Day 393	(Day 379 - Day 406)
Day 421	(Day 407 - Day 434)
Day 449	(Day 435 - Day 462)
Day 477	(Day 463 - Day 490)

The following visits will not be remapped: Screening, IP Discontinuation, 30/90 Day Follow-up, Survival Follow-up.

In case several visits occur into the same windows the following rule is to be applied:

- For by-visit table, we will consider the mean of available assessments.
- For Shift table, we will consider either Minimum or Maximum available value depending on the direction.

4.2.3 Definition of Baseline and Post-baseline Assessments

A baseline assessment will be defined as the last assessment performed prior to the first dose of study treatment (C0D1). While many of these assessments will be performed on the day of the first dose, others will be performed during screening. If a patient is missing an assessment typically performed on the day of the first dose, screening values may be substituted as baseline.

Patients treated with RXC004 monotherapy (arm A) that radiologically progress as per RECIST1.1 at the first 'on treatment' scan, may be treated with RXC004 + Nivolumab combination. Accordingly, the following groups of analyses have to be defined to clarify which patients and which information in arm A will be utilized:

- **Arm A (RXC004 monotherapy):** this group will include information for all patients enrolled in arm A.
- **Arm A1 (RXC004 monotherapy):** this group will include information of all patients enrolled in Arm A who were on monotherapy throughout the study - ie. subjects who did not radiologically progressed at the first scan (week 8) or who radiologically progressed

at the first scan (week 8) but remained on monotherapy or who withdrew before the first scan.

- **Arm A2 (RXC004 + Nivolumab):** this group will include information of patients enrolled in arm A who radiologically progressed at the first scan (Week 8) and then switch to receive combination therapy of RXC004 + Nivolumab either at Week 8 or later. The last scan before the switch to combination treatment will be set as the arm A2 baseline RECIST1.1 scan for the combination treatment. The date of the last scan before switching to combination treatment will also be used to determine the arm A2 baseline date for all the efficacy endpoints except OS. OS will keep the same baseline regardless of the progression. For assessments other than efficacy, Arm A2 summaries, will include data from start of monotherapy until end of combination treatment.
- **Arm B (RXC004 + Nivolumab):** this group will include information on all patients enrolled in arm B.

Some patients with symptomatically stable disease may continue treatment after the initial RECIST 1.1 - defined progression, until symptomatic/clinical progression or a second RECIST 1.1 PD assessment (relative to the initial RECIST1.1 progression, for a given study treatment).

Change from baseline is derived where both baseline and post-baseline values are available:

- Absolute Change from baseline = post-baseline value – baseline value
- Relative Change from baseline (%) = $[(\text{post-baseline value} - \text{baseline value}) / \text{baseline value}] * 100$

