\*\*~~CCI~~ [REDACTED], ideally from the same site of disease (e.g. liver, lymph node etc) that the 'on treatment' biopsy will be taken from, and taken after completion of all prior standard of care treatments will be accepted as a baseline biopsy.

- 8 Patients with adequate organ functions as described below;
  - AST/ALT  $\leq$  2.5X ULN (upper limit of normal) [with no underlying Liver Metastasis]
  - AST/ALT  $\leq$  5 X ULN [with underlying Liver Metastasis]
  - Total Bilirubin  $\leq$  1.5 X ULN
  - Serum Creatinine  $\leq$  1.5 X ULN
  - ANC  $\geq$  1.5  $\times$  10^9/L
  - Platelets  $>$  100  $\times$  10^9/L
  - Hb  $>$  8.5g/dL (with or without transfusional support)
  - Calculated creatinine clearance (CrCL)  $\geq$  60 mL/min as determined by Cockcroft Gault (using actual body weight).

Males:

$$\text{CrCL} = \frac{\text{Weight (kg)} \times (140 - \text{Age})}{72 \times \text{serum creatinine (mg/dL)}}$$

Females:

$$\text{CrCL} = \frac{\text{Weight (kg)} \times (140 - \text{Age})}{72 \times \text{serum creatinine (mg/dL)}} \times 0.85$$

- 9 Female patients of childbearing potential must have a negative pregnancy test prior to start of dosing
- 10 Female patients of childbearing potential and male patients with female partners of childbearing potential must agree to use a highly effective method of contraception during the study and for at least 5 months after the last dose of study drug. See Section 5.3.1 for details of acceptable methods of contraception

**For patients on RXC004 monotherapy treatment (Arm A) the following inclusion criteria will also apply to enter the RXC004 + nivolumab treatment phase;**

11. Patients must have had documented RECIST1.1 defined radiological progression on RXC004 monotherapy treatment on the first scheduled scan (week 8 +/- 1 week)
12. Patients must receive Cycle 1 Day 1 of combination study treatment within 28 days of the first scheduled scan (week 8 +/- 1 week) showing RECIST1.1 defined radiological progression, or for clinically stable patients that remain on RXC004 after RECIST1.1 defined radiological progression, within 28 days of the most recent scan showing further radiological progression or confirmation of the week 8 RECIST1.1 progression (see Section 7.1.1 and Appendix D for more details)

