4.11.3.3 Overall Survival

OS is defined in Section [3.2.1.6](#).

Kaplan-Meier analyses will be conducted for arm A and arm B (in the same plot) and separately for arm A2. Survival plots will be produced to present Kaplan-Meier estimated curves.

OS will be listed for all patients in the FAS.

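### Arm A2 PFS is timed from the last scan before the switch, so up to 28 days before the first nivolumab dose count as progression-free time in a group labelled as combination therapy

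*SAP*

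**What the plan says.** - **A2 baseline (SAP 4.2.3).** The last scan before the switch is the A2 RECIST baseline, and its date "will also be used to determine the arm A2 baseline date for all the efficacy endpoints except OS". For survival, "OS will keep the same baseline regardless of the progression".
- **Gap to treatment (Protocol 5.1, criterion 12).** "Patients must receive Cycle 1 Day 1 of combination study treatment within 28 days of the first scheduled scan". Clinically stable patients who stay on RXC004 and switch later have the same 28 days, counted from their most recent scan.
- **PFS in general (SAP 3.2.1.5).** The clock runs from C0D1. No A2 version of the formula is given.
- **DCR (SAP 3.2.1.3).** The main version needs stable disease to 16 weeks, equated with two scheduled scans: "any scan that is at least 15 weeks after starting treatment will be considered acceptable for the evaluation of response". The additional 8-week version equates to one scan and accepts it from 7 weeks.
- **Study days (SAP 4.2.1).** For switchers the day count restarts at the first combination intake.
- **Tumour change (SAP 4.11.3.1).** A2 change is referenced to Week 8, although 4.2.3 allows the switch, and so the baseline scan, to be later.
- **Scan calendar (Protocol 1.2, Table 1, combination phase).** "On study tumour assessments should continue q8w +/- 1 week (relative to first dose of IP) for the first 56 weeks". It is not reset at the switch.
- **OS.** SAP 3.2.1.6: "OS is defined as the time from the first day of study treatment (Day 1) until death due to any cause". SAP 4.11.3.3: "Kaplan-Meier analyses will be conducted for arm A and arm B (in the same plot) and separately for arm A2". SAP 4.15 then says OS will be listed without a summary.

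**The concern.** A scan is a sensible reference for lesion size but a poor time zero for a treatment that has not begun. A patient who dies or becomes ineligible between the scan and combination C1D1 never enters A2. The interval is therefore immortal time for death. It also contains no documented radiological progression, because any further scan in the interval would itself become the last pre-switch scan.

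The SAP does not handle the other arms this way. The screening scan in Arms A and B may also precede treatment by up to 28 days (Protocol 5.1, criterion 6), yet their PFS starts at first dose.

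Protocol 9.4.1 commits to presenting ORR, DCR and PFS separately for the sequential-combination patients, of whom there may be up to 20. They are the trial's only evidence on adding nivolumab after progression on RXC004. Readers will set their PFS beside Arm B's, which carries the same treatment label but a different clock.

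**Working it through.** The documents give no A2 sample size, event count or target, so there is no planned figure to reproduce. The check is date arithmetic plus an illustration.

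**Inputs**
- Scan-to-dose gap d: 0 to 28 days (Protocol 5.1, criterion 12). No distribution of actual gaps is given.
- Month = 30.4375 days (SAP 4.11.3.2).
- Median PFS of 2 months = 60.875 days. This is an assumption, borrowed from the third-line background figure in Protocol 2.3.3.
- Exponential shape and a common d for all patients: also assumptions.

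**PFS.** For each patient, PFS from the scan = PFS from combination C1D1 + d. With median m from C1D1, the displayed median is (m + d)/30.4375 months, and displayed PFS at time t is 0.5^((t − d)/m). Three months is 91.31 days.

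| Gap d | Displayed median | 3-month PFS |
|---|---|---|
| 0 days | 60.875/30.4375 = 2.00 months | 0.5^(91.31/60.875) = 35.4% |
| 14 days | 74.875/30.4375 = 2.46 months | 0.5^(77.31/60.875) = 41.5% |
| 28 days | 88.875/30.4375 = 2.92 months | 0.5^(63.31/60.875) = 48.6% |

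The 28-day case lengthens the median by 28/60.875 = 46%. For assumed medians of 1.5 and 4 months the figure is 61% and 23%.

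**DCR exposure.** At the maximum gap, the earliest scan accepted for the 16-week version follows 15 − 4 = 11 weeks of combination. For the 8-week version it follows 7 − 4 = 3 weeks.

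**What happens if the DCR thresholds are moved to C1D1.** After a week-8 switch, nominal scans fall 8, 16 and 24 weeks after the A2 baseline scan. Counted from C1D1 they fall at 6, 14 and 22 weeks when d = 14, and at 4, 12 and 20 weeks when d = 28. Once d exceeds 16 − 15 = 1 week, the second nominal scan misses the 15-week threshold and a third is needed. On the same exponential:
- control to 15 weeks from C1D1, the intended quantity: 0.5^(105/60.875) = 30%;
- scan-date clock: 0.5^(91/60.875) = 35% at d = 14, and 0.5^(77/60.875) = 42% at d = 28;
- threshold moved to C1D1: 0.5^(154/60.875) = 17% at d = 14 (control to 22 weeks), and 0.5^(140/60.875) = 20% at d = 28 (control to 20 weeks).

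At d = 14 the scan-date rule is about 5 points high and the moved threshold about 13 points low. For the 7-week threshold at d = 14, the intended figure is 57%, the scan-date clock gives 67%, and the moved threshold gives 0.5^(98/60.875) = 33%.

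**The case against.** **The size is overstated.** The illustration assumes nothing happens in the gap. Death and documented progression are indeed excluded, but tumour growth in the gap accumulates and is read at the next scan, which counts against A2. Twenty-eight days is an eligibility ceiling, and the 2-month median belongs to other drugs. All of this stands. The displayed PFS is longer by exactly d than it would be from first dose, but how much of that is net bias is not established.

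**The clock is not settled.** Read literally, SAP 3.2.1.5 gives A2 a C0D1 origin, under which the qualifying week-8 progression would itself be the event. SAP 3.2.1.3 counts from starting treatment, and 4.2.1 restarts days at the first combination intake. This also stands, but it does not rescue the plan: 4.2.3 is the only text that sets an A2 efficacy baseline, and it names the scan.

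**A2 carries little weight.** It has no hypothesis or decision rule, no formal between-arm comparison is planned, and its Kaplan-Meier curve needs at least 8 events (SAP 4.2.7). Its patients are selected progressors, so A2 and Arm B would not be alike under any clock. Arm B's own PFS includes the 3 to 7 days of Cycle 0 without nivolumab. These points limit the importance of the error without removing it.

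**Readings the documents do not support.** A reader might infer that the SAP reports inflated survival on the combination. A C0D1 origin would add 7 to 13 guaranteed weeks after a week-8 switch (scan at week 7 to 9 plus 0 to 4 weeks), but only if the A2 curve in 4.11.3.3 is produced. SAP 4.15 says OS is only listed, SAP 6.2 does not name OS for A2, and Protocol 9.4.1 does not promise it. A reader might also infer that the DCR thresholds should follow PFS to C1D1. On the fixed scan calendar that over-corrects, as the working shows. ORR gains nothing from the clock.

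**Conclusion.** The point holds for PFS. As written, 4.2.3 credits A2 with 0 to 28 days of guaranteed death-free time before nivolumab, which the SAP does not do in Arms A and B. That follows from the definitions alone.

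The size rests on assumptions: with an exponential 2-month median and no events in the gap, up to 0.46 month is added to the median for a 14-day gap and 0.92 month for a 28-day gap. These are upper bounds on the bias.

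For DCR, the defect is an unstated A2 origin and undisclosed time on combination at the qualifying scan. For OS, it is an unresolved conflict between 4.11.3.3 and 4.15. The Arm A and Arm B primary endpoints are untouched, since switchers count as progressed in Arm A. The correction is worth making because it is cheap, but no primary conclusion depends on it.

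**What to change.** 1. **PFS.** In SAP 4.2.3, keep the last pre-switch scan as the A2 RECIST reference for tumour size, and set the A2 PFS origin to the first combination dose (combination C1D1). Add an A2 line to 3.2.1.5, including its rules that count from first dose.
2. **DCR.** Keep the scheduled-scan definition: two scans after the A2 baseline scan, or one for the 8-week version. State that origin explicitly for A2. Report the scan-to-dose gap and the time on combination at the qualifying scan.
3. **Consistency.** Align 3.2.1.3, 3.2.1.5, 4.2.1, 4.2.3 and 4.11.3.1, including Week 8 against last pre-switch scan for tumour change.
4. **OS.** Decide between 4.11.3.3 and 4.15. If any A2 curve is drawn, start it at combination C1D1 or label it as survival of the whole sequence from C0D1.

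The cost is SAP wording, one date variable and two descriptive summaries, with no new data. Each A2 patient's PFS becomes shorter by that patient's gap. The DCR will still include some time before nivolumab, but the reader will be able to see how much.
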